### Protocol Amendment 1: June 2018

#### Overall Rationale for the Amendment:

The protocol was amended to provide clarification of the exclusion criteria and of Appendix 5.

Section No. and Name	Description of Change	Brief Rationale
Section 6.2 Exclusion Criteria	Revised Exclusion Criterion 7 to state: “Lifetime history of nonresponse to $\geq 2$ antidepressants after adequate trials (adequate treatment is defined as at least 6 weeks at an adequate dose(s) based on approved package insert recommendations).”	For clarity
Section 12.5: Appendix 5 Contraceptive Guidance and Collection of Pregnancy Information	Clarified description of acceptable contraceptive methods.	For clarity

### 3 List of Abbreviations and Definition of Terms

**Table 3-1 Abbreviations and Definitions of Terms**

Abbreviation/Term	Definition
AE	adverse event
ANCOVA	analysis of covariance
CFB	change from baseline
CGI-S	Clinical Global Impressions–Severity
C-SSRS	Columbia–Suicide Severity Rating Scale
eCRF	electronic case report form
ECG	electrocardiogram, electrocardiographic
ET	early termination
mITT	modified intent-to-treat
LOCF	last observation carried forward
LS	least squares
MADRS	Montgomery–Åsberg Depression Rating Scale
MDD	major depressive disorder
MedDRA	Medication Dictionary for Regulatory Activities
MMRM	mixed-effects model for repeated measures
PCS	potentially clinically significant
PK	pharmacokinetic
PID	participant identification
PT	preferred term
QTc	QT interval corrected for heart rate
QTcB	QT interval corrected for heart rate using the Bazett formula ( $QTcB = QT/(RR)^{1/2}$ )
QTcF	QT interval corrected for heart rate using the Fridericia formula ( $QTcF = QT/(RR)^{1/3}$ )
SAE	serious adverse event
SAP	statistical analysis plan
SI	Le Système International d'Unités (International System of Units)
SOC	system organ class
TEAE	treatment-emergent adverse event
WHO	World Health Organization

## 4 Introduction

This statistical analysis plan (SAP) details comprehensive, technical specifications of the statistical analyses of the efficacy and safety data outlined and/or specified in the final protocol of Study 3125-201-002 (version dated 02 March 2018) and the most recent amendment (version #1 dated on 08 Jun 2018). Specifications of tables, figures, and data listings are contained in a separate document.

This study is a multicenter, randomized, double-blind (with a single-blind placebo lead-in), placebo-controlled, parallel-group, fixed-dose, 3-week study in participants with major depressive disorder (MDD). The study will include a total of 10 visits and will be approximately 5 weeks in duration:

[figure not shown]
- Up to 1-week screening period
- 3-week double-blind treatment period
- 1-week safety follow-up period

Approximately 250 participants are planned for enrollment in the double-blind treatment period (50 participants each in the AGN-241751 and placebo groups). Participants will be randomized in a ratio of 1:1:1:1:1 to 1 of 5 treatment groups: 0.25 mg, 1 mg, 3 mg, 10 mg dose AGN-241751, and placebo.

Aside from the single-blind screening period and double-blind treatment period, there is an additional single-blind element to this study (blinded to the participant). AGN-241751 is being developed for once-weekly dosing; however, in order to minimize participant's expectations and control for placebo response, treatment will be presented to participants as oral daily dosing. Each treatment kit (dispensed once weekly) in the double-blind treatment period will contain 2 bottles: Bottle 1 will contain a single dose of double-blind study treatment and Bottle 2 will contain multiple doses single-blind placebo tablets (blinded to the participant). At Visit 2 (Day 1), Visit 5 (Day 8), and Visit 8 (Day 15), site staff will give the participant the single dose of double-blind study treatment from Bottle 1 to take by oral ingestion in the clinic (ie, the first dose of study treatment for that week). Site staff will give Bottle 2, which contains the single-blind placebo tablets, to the participant with the instruction to take 1 tablet daily by oral ingestion for the remainder of that week. To maintain consistency, study treatment at Visit 1 (single-blind placebo lead-in) will be dispensed in the same manner; the single dose of single-blind study treatment from Bottle 1 will be given to the participant for oral ingestion in the clinic, and then, Bottle 2 containing single-blind placebo tablets will be dispensed for the participant to take 1 tablet daily by oral ingestion through the remainder of the week.

During the first 2 weeks of the double-blind treatment period, participants will have 3 study visits per week. The visits will occur in the following pattern: in-clinic treatment day, 1 day following the in-clinic treatment day, 4 days following the in-clinic treatment day, and 7 days following the in-clinic treatment day (which is the next in-clinic treatment day). If necessary, study visits may be conducted up to 2 days before or after the scheduled visits with the exception of visits that are 1 day apart (ie, Visits 2 and 3 must be conducted 1 day apart; and Visits 5 and 6 must be conducted 1 day apart). Visit 8 will be conducted 7 days following the second in-clinic treatment day. All participants who receive study treatment must complete Visit 9/ET. Participants will enter a 1-week safety follow-up period and return for Visit 10. Participants who prematurely discontinue from the study before completing 3 weeks of double-blind treatment should enter the 1-week safety follow-up period. Additional follow-up visits may be scheduled within 30 days, if necessary for safety reasons.

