#### Protocol Amendment 2: May 2019

#### Overall Rationale for the Amendment:

The protocol was amended to incorporate regulatory agency feedback on statistical analysis.

Section No. and Name	Description of Change	Brief Rationale
1 Synopsis	Added that framework for estimands will be discussed in Section 10.1	Based on updated regulatory requirements for statistical analysis that requires inclusion of estimands.
4. Objectives and Endpoints	This section was updated to clarify endpoints for the additional analysis to include all days where MADRS, CGI-S, etc were evaluated that were not part of primary or secondary analysis	Clarification to the protocol
10.1 Estimands Framework	This section was added, including subsections, and provides an estimand framework for the primary and secondary endpoints	As above
10.4.1 Efficacy Analysis	Removed LOCF calculations and changed small center will be defined as a center with fewer than 2 participants (instead of 5 participants) in the mITT Population	As above and to align with other studies in the program
10.4.1.1 Primary and Secondary Endpoint	Added reference to estimands	As above
10.4.1.2 Primary and Secondary Analysis	Updated statistical methods, including removal of LOCF and ANCOVA from analysis and replaced with a sensitivity analysis using the MI approach under MNAR assumptions	As above
10.4.2.2 Clinical Laboratory	Clarified language regarding non-PCS baseline values	Clarification

Section No. and Name	Description of Change	Brief Rationale
Assessments		
10.4.2.3 Vital Signs	Clarified language regarding non-PCS baseline values	Clarification
12.1 Appendix 1	Updated abbreviations based on changes to body	To align with other changes in the protocol
12.5 Appendix 5	Removed bilateral tubal ligation as the type of surgical sterilization for female partners of male study subjects.	To align with other studies in the program.

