#### **10.4.1. Efficacy Analyses**

The efficacy analyses will be based on the mITT population. Baseline for efficacy is defined as the last nonmissing efficacy assessment before the first dose of study treatment. All statistical tests will be 2-sided hypothesis tests performed at the 5% level of significance for main effects. All confidence intervals will be 2-sided 95% confidence intervals, unless stated otherwise.

For efficacy analyses in which study center is a factor, a small center will be defined as a center with fewer than 2 participants in the mITT Population. All the small centers will be pooled to form a pseudo-center. If the pseudo-center is still a small center, it will be pooled with the smallest non-small center. If there is more than one smallest non-small center, the small pseudo-center will be pooled with the smallest non-small center that has the largest center number.

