#### 10.4.1.2. Primary and Secondary Analyses

The primary analysis for the primary and secondary endpoints will be performed using a MMRM with treatment group, visit, pooled study center, and treatment group-by-visit interaction as fixed effects and the baseline value and baseline value-by-visit as covariates. An unstructured covariance matrix will be used to model the covariance of within-participant scores. If the model fails to converge based on the unstructured covariance matrix, then structures of Heterogenous Toeplitz, Toeplitz, and Compound Symmetry will be applied, in the specified order, until the model converges. The Kenward-Roger approximation will be used to estimate denominator degrees of freedom (Kenward and Roger 1997). These analyses will be performed based on all postbaseline scores using only the OCs without imputation of missing values.

[figure not shown]
In addition, a sensitivity analysis using the multiple imputation (MI) approach under missing not at random (MNAR) assumptions will be performed on the primary and secondary efficacy parameters.

Detailed methods and procedures for the above outlined missing data-derived sensitivity analyses will be documented in the final SAP prior to the study database lock.

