## **10 Efficacy Analyses**

The efficacy analyses will be based on the mITT population. The last-observation-carried-forward (LOCF) approach will be used to impute missing postbaseline values. Baseline for efficacy is defined as the last nonmissing efficacy assessment before the first dose of study treatment. All statistical tests will be 2-sided hypothesis tests performed at the 5% level of significance for main effects. All confidence intervals will be 2-sided 95% confidence intervals, unless stated otherwise.

For efficacy analyses in which study center is a factor, a small center will be defined as a center with fewer than 5 participants in the mITT Population. All the small centers will be pooled to form a pseudo-center. If the pseudo-center is still a small center, it will be pooled with the smallest non-small center. If there is more than one smallest non-small center, the small pseudo-center will be pooled with the smallest non-small center that has the largest center number.

The rater-administered MADRS will be used for the efficacy analyses.

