## 10.1 Primary and Key Secondary Efficacy Endpoints

Primary efficacy endpoint:

- Change from baseline in MADRS total score at 1 day after first dose

Key secondary efficacy endpoint:

- Change from baseline in MADRS total score at Week 3

[figure not shown]
The primary analysis for the primary and key secondary endpoints will be performed using a mixed-effects model for repeated measures (MMRM) with treatment group, visit, pooled study center, and treatment group-by-visit interaction as fixed effects and the baseline value and baseline value-by-visit as covariates. An unstructured covariance matrix will be used to model the covariance of within-participant scores. The Kenward-Roger approximation will be used to estimate denominator degrees of freedom (Kenward and Roger 1997). These analyses will be performed based on all postbaseline scores using only the OCs without imputation of missing values.

In addition, a sensitivity analysis using the LOCF approach will be performed on the primary efficacy and key secondary parameters. The between-treatment group comparisons will be performed by means of an analysis-of-covariance (ANCOVA) model with treatment group and study center as factors and the baseline MADRS total score as the covariate. The LOCF approach will be used to impute missing postbaseline values, provided that at least 1 postbaseline assessment is available. Missing values between the baseline and the first nonmissing postbaseline will be imputed with the baseline value. If all the postbaseline values are missing, the baseline value will not be carried forward. Only the total score of a parameter will be imputed using the LOCF approach; individual item scores will not be carried forward.

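### The supplied SAP is written to protocol Amendment 1: it has no MNAR multiple imputation and pools centers by a different threshold from the current protocol; separately, it leaves out the protocol's QTc increase counts

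*SAP*

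**What the plan says.** SAP 4 (Introduction) states that it details the March 2018 protocol and "the most recent amendment (version #1 dated on 08 Jun 2018". The protocol's document history goes one step further, to "Protocol Amendment 2: May 2019", and gives regulatory feedback on the statistical analysis as the reason for that amendment.

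**Sensitivity analysis.** Protocol 10.4.1.2 says that "a sensitivity analysis using the multiple imputation (MI) approach under missing not at random (MNAR) assumptions will be performed" for the primary and secondary efficacy parameters, and that the methods for these "sensitivity analyses will be documented in the final SAP prior to the study database lock". SAP 10.1 says instead that "a sensitivity analysis using the LOCF approach will be performed on the primary efficacy and key secondary parameters", with an ANCOVA on the imputed scores.

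**Small centers.** Protocol 10.4.1: "a small center will be defined as a center with fewer than 2 participants in the mITT Population". SAP 10: "a small center will be defined as a center with fewer than 5 participants in the mITT Population". Pooled study center is a fixed effect in the primary MMRM in both documents.

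**QTc.** Protocol 10.4.2.4 requires, by treatment group, the number and percentage of participants with a QTc increase above 30 and up to 60 msec, and above 60 msec, with a listing of those above 30. SAP 11.4 contains neither. It refers to change-from-baseline criteria in Table 11-4, but that table has only upper limits on the observed value (above 500 msec for QTcB and QTcF).

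**The concern.** An analyst working from this SAP alone would run a sensitivity analysis that the current protocol no longer contains and would not run the one it requires. Neither document gives an imputation model, a departure from MAR, or a rule for reading the result. If the SAP is not updated, those choices would have to be made outside the plan, possibly after data have been seen. The same analyst could also build a different center factor for the primary model from the one the protocol defines.

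The MNAR analysis is not an empty requirement for the primary endpoint. The mITT population needs only one postbaseline MADRS, and there is a 4-hour assessment on Day 1, so a participant can be in mITT without a Day 2 score.

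On QTc, participants with a large rise that stays at or below 500 msec would not appear in any categorical count.

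**Working it through.** **1. Side-by-side comparison of the current texts**

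| Item | Protocol (Amendment 2) | SAP | Relation |
|---|---|---|---|
| Sensitivity analysis, primary and key secondary | MI under MNAR; details left to the SAP (10.4.1.2) | LOCF with ANCOVA; no MI or MNAR, and neither term in the abbreviation list (10.1, Table 3-1) | Conflict; method unspecified |
| Small center | Fewer than 2 (10.4.1) | Fewer than 5 (10) | Conflict |
| Non-convergence | Ordered list of three simpler structures (10.4.1.2) | Unstructured only (10.1) | Omission |
| General LOCF statement | None | All missing postbaseline values (10), beside an MMRM without imputation (10.1) | SAP internally loose |
| Changes from protocol | n/a | None declared (17) | Not correct against Amendment 2 |
| QTc increase counts and listing | Required (10.4.2.4) | Absent (11.4) | Omission |

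The amendment log explains the cause of two rows: "Removed LOCF calculations and changed small center will be defined as a center with fewer than 2 participants (instead of 5 participants". Every row stands on current section text without it. The log lists no ECG change, so the QTc gap is not shown to come from the amendment.

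**2. How the center thresholds differ**

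Inputs: about 250 participants and about 20 sites (protocol synopsis), so 250/20 = 12.5 per site. The spread of site sizes is not given. Assume it is even (Poisson) or uneven (gamma shape 4, 2 or 1).

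Expected number of sites with 2-4 participants = 20 x P(2 to 4): 0.11 even; 1.79, 2.87 and 3.54 uneven.

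These sites are classified differently, but they are not the only ones affected. A pseudo-center that is still small is merged with the smallest non-small center. Two invented examples:

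- One site has 3 participants, the next smallest has 6, and the rest are larger. The protocol keeps both separate. Under the SAP the pseudo-center of 3 is still below 5 and is merged with the site of 6.
- Three sites have 1, 3 and 4, and the rest are larger. The SAP pools all three (1 + 3 + 4 = 8). Under the protocol the single participant joins the site of 3, and the site of 4 stands alone.

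In 4,000 simulated allocations with both pooling rules applied in full:

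- The groupings differ in about 9% of trials with even enrollment and 84-98% with uneven enrollment (shape 4 to 1).
- A site of 5 or more is regrouped in about 9% (even) and 30% (shape 4).
- A single-participant site changes group in 74% at shape 1.
- Mean number of center levels, SAP against protocol: 18.6 and 19.8 (shape 4), 17.1 and 19.1 (shape 2), 14.7 and 17.7 (shape 1).

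**3. What that could do to a dose-placebo contrast (illustration only)**

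A single-visit ANCOVA stood in for the MMRM, with assumed residual SD 9 and site SD 0-3. The absolute difference between the two contrasts has median 0.00 and 95th percentile 0.03-0.05 points with even enrollment, and median 0.04-0.12 and 95th percentile 0.30-0.51 points with uneven enrollment. For scale, SE = 9 x sqrt(2/50) = 1.8 points.

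**4. What MNAR departures could do (illustration only)**

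Shift = (difference in missing fraction between arms) x (assumed penalty for missing participants relative to MAR).

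- Week 3, assuming a 0-5 percentage-point difference and a 5-10 point penalty: up to 0.05 x 5 = 0.25 or 0.05 x 10 = 0.50 points. At SE 1.8 the larger is 0.50/1.8 = 0.28 SE. With SD 7 or 11 the SE is 1.4 or 2.2, and the ratio 0.36 or 0.23.
- Day 2, each missing participant in one arm of 50: 1/50 x 5 = 0.1 to 1/50 x 10 = 0.2 points.

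**5. Covariance**

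Eight postbaseline MADRS assessments (4 hours; Days 2, 5, 8, 9, 12, 15, 22) give 8 x 9/2 = 36 unstructured parameters, against 15, 8 and 2 for the three fallback structures.

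**6. QTc**

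With only values above 500 msec flagged, a rise of up to 500 - 400 = 100 msec from a baseline of 400 is not counted. A rise of 60 from 440 ends at exactly 500, so no rise of 30-60 msec is counted from a baseline at or below 440.

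**The case against.** The strongest objection is that this SAP may not be the governing one. Its title page and date are not available, it predates or overlooks Amendment 2, and the protocol itself expects a final SAP before database lock. That stands. A reader might infer that the trial was analyzed without the MNAR analysis, or that the sponsor's declaration of no changes in SAP 17 was wrong when made. The documents support neither: a later SAP may exist, and the declaration may have been right against Amendment 1.

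A reader might also infer that the primary analysis differs or uses LOCF. It does not. Both documents specify an MMRM on observed cases with the same fixed effects and covariates, and SAP 10.1 and 10.3 name the analyses to which LOCF applies. Population, endpoints, alpha and the multiplicity text also match.

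Nor are the threshold and the covariance fallback unspecified: the protocol prespecifies both. Only the MNAR method lacks detail in both documents, and it is a sensitivity analysis.

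The at-most-5% figure in protocol 10.1.3 cannot be used to bound the MNAR shift. It is an overall expectation of not receiving later doses, not a difference between arms and not a rate of missing Week 3 scores.

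On QTc, table and listing specifications are in a separate document not supplied, so the counts may be planned there. Change from baseline is still summarized descriptively. What remains is that the SAP text does not plan the counts, and that 11.4 and Table 11-4 disagree with each other.

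**Conclusion.** The supplied SAP does not match the current protocol. Two points are real conflicts: LOCF/ANCOVA in place of an MNAR multiple imputation whose method is nowhere specified, and fewer than 5 against fewer than 2 for the center factor in the primary model. Three are minor: the omitted fallback order, the over-broad LOCF sentence in SAP 10, and the entry in SAP 17. The QTc omission and the mismatch with Table 11-4 are a separate safety-reporting item.

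This should be fixed before database lock, but it does not put the primary analysis in doubt. The numerical effect is usually small. The grouping frequencies depend on an assumed spread of site sizes. The shifts in points depend further on an SD, site variation and dropout pattern that the documents do not give, so they indicate scale and are not bounds. The main consequence is that a required analysis would be without a prespecified method.

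**What to change.** Before database lock, re-issue the SAP against Amendment 2, or confirm that a later version already does the following:

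- Replace the LOCF/ANCOVA sensitivity analysis for the primary and key secondary endpoints with a fully specified multiple imputation under MNAR: imputation model, departure from MAR, number of imputations and how the result will be read. A delta-adjusted tipping point is one suitable form, and it should fit the hypothetical estimand in protocol 10.1.3.
- Set the small-center threshold to fewer than 2.
- Add the protocol's covariance fallback order.
- Limit the general LOCF sentence in SAP 10 to the analyses that name LOCF.
- Add the QTc increase counts and listing to 11.4, and make 11.4 agree with Table 11-4 by adding change criteria or deleting the reference.
- List any departure that is kept, with its reason, in section 17.

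The cost is a SAP revision and some programming. No protocol amendment and no new data are needed.

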**Figure 4-1 Study Design**

## 5 Study Objectives

The primary objective is to evaluate the efficacy, as measured by improvement in MADRS total score, at 1 day post initial oral dose of AGN-241751 compared with placebo in participants with MDD. The key secondary objective is to evaluate the efficacy at Week 3 of AGN-241751 administered orally once a week compared with placebo in participants with MDD.

**Table 5-1 Schedule of Activities (SoA)**

Visit	Single-blind Placebo Run-In Period	Double-blind Treatment Period									Safety Follow-up Period
	1 (Screening)	2 (Baseline)	2a	3	4	5	6	7	8	9/ETa	10
Study Day	up to -7 days	1	4 hrs post dose	2 (1 day post dose)	5	8	9	12	15	22	29
Informed consent	x										
Medical (surgical, neurologic) and psychiatric histories	x										
Prior medication history	x										
Inclusion/exclusion	x	x									
Randomization assessment		x									
Clinical laboratory determinations b	x									x	
Urine drug screen	x									x	
Serum pregnancy test	x									x	
Vital signs c	x	x	x	x	x	x	x	x	x	x	x
ECG	x									x	
Physical examination	x									x	
DxV	x										
SCID	x										
MADRS	x	x	x	x	x	x	x	x	x	x	
CGI-S	x	x	x	x	x	x	x	x	x	x	
BPRS+	x	x				x				x	
CADSS	x	x				x				x	
C-SSRS	x	x	x	x	x	x	x	x	x	x	x
SDC	x									x	
C-VISA	x										

	Single-blind Placebo Run-In Period	Double-blind Treatment Period									Safety Follow-up Period
Visit	1 (Screening)	2 (Baseline)	2a	3	4	5	6	7	8	9/ET a	10
Study Day	up to -7 days	1	4 hrs post dose	2 (1 day post dose)	5	8	9	12	15	22	29
AEs		x	x	x	x	x	x	x	x	x	x
Concomitant medications	x	x	x	x	x	x	x	x	x	x	x
PK sampling		x (1 hr, 2 hrs, and 4 hrs post dose)				x 1 sample (15 min to 3 hrs post dose)					
Study treatment administration in the clinic	x (single-blind placebo)	x				x			x		
Study treatment compliance		x		x	x	x	x	x	x	x	

Screening procedures may be conducted on up to 2 separate dates where necessary to accommodate participant and site schedule; however, every effort should be made to conduct all procedures as early as possible in the screening period. The rater-administered MADRS and computer-administered MADRS must be collected on the same date. At Visit 1 (Screening), the computer-administered MADRS will be conducted prior to the rater-administered MADRS. At all other visits, the rater-administered MADRS will be conducted first.

If necessary, study visits may be conducted up to 2 days before or after the scheduled visits except for visits that are 1 day apart (ie, Visits 2 and 3 must be conducted 1 day apart, and Visits 5 and 6 must be conducted 1 day apart).

AE = adverse event; BPRS+ = Brief Psychiatric Rating Scale - Positive Symptoms Subscale; CADSS = Clinician Administered Dissociative States Scale; CGI-S = Clinical Global Impressions-Severity; C-SSRS = Columbia-Suicide Severity Rating Scale; C-VISA = Clinical Validation Inventory for Study Admission; DSM = *Diagnostic and Statistical Manual of Mental Disorders*; DxV = Diagnostic Validation; ECG = electrocardiogram; ET = Early Termination; MADRS = Montgomery-Åsberg Depression Rating Scale; PK = pharmacokinetic; SCID = Structured Clinical Interview for DSM disorders; SDC = Symbol Digit Coding

a Performed for all participants, including those prematurely discontinued after randomization. Clinically significant findings upon termination should be followed until the condition returns to prestudy status or can be explained as unrelated to study treatment. If necessary, additional follow-up visits can be scheduled.

b Participants will be requested to fast overnight or for at least 8 hours before arriving at the study center for appointments involving the collection of clinical

laboratory blood tests. Clinical laboratory tests can be done at any visit for safety reasons at the discretion of the investigator.

- c Height will only be measured at Visit 1 (Screening); pulse rate, blood pressure, temperature, and body weight will be assessed at every visit. Blood pressure and pulse will be assessed while the participant is supine and standing.
- d PK sampling is optional. For participants who consent to participate, samples will be collected at Visit 2/2a (Day 1) at 1 hour ( $\pm$  15 minutes), 2 hours ( $\pm$  15 minutes), and 4 hours ( $\pm$  15 minutes) post dose. At Visit 5 (Day 8), a single sample will be collected any time from 15 minutes to 3 hours post dose; site staff should record the time of the prior meal taken by the participant before the PK sample collection, whenever possible.

